## **8. RESEARCH QUESTION AND OBJECTIVES**

The overall objective of the present IPF Registry is to gain further insight on the characteristics, management, disease progression and the outcomes of patients with IPF, as diagnosed and treated under real-world, clinical practice conditions in Greece.

More specifically, this registry will be used to:

- Provide a comprehensive clinical picture of IPF
- Track access to health care and cost of caring for IPF patients over time
- Examine the implementation of treatment guidelines [2], used on patients diagnosed with IPF, according to the existing diagnosis guidelines [1]
- Characterization of patients on different treatments

Furthermore, this project aims to provide information regarding survival and mortality causes, IPF exacerbations as well as IPF patient co-morbidities including myocardial infarction, CNS infarction, other arterial thromboembolic events, deep vein thrombosis, hemorrhage, gastrointestinal perforation and pulmonary hypertension (please refer to [Annex 3](#)). In addition, data regarding IPF patient hospitalization will be collected and evaluated with regards to potential respiratory causes, and there will be documentation of treatment patterns and economic aspects. Patients will be followed up for 2 years and information regarding IPF treatment changes since the last visit will be collected.

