### **9.3.2 Withdrawal Criteria**

The patients reserve the right to withdraw consent at any time during the study, without the need for justification and without any impact on their future treatment and care.

Withdrawal of consent means that the patient does not wish or cannot continue to participate in the study any more.

The reasons for withdrawal may include the following:

- Patient or legally accepted representative withdraws informed consent for participation in the study.
- Inclusion or possible participation in any clinical trial, any time within the follow up period of the study, in which the patient has been exposed or is going to be exposed to an investigational product (pharmaceutical product or medical device) or intervention.
- The patient was erroneously included in the registry
- Decision of the investigator/physician
- Important deviation/divergence from the protocol.

The Clinical Monitor at BI or BI's designees must be immediately notified if a patient is discontinued prematurely for any of the instances reasons cited above.

Patients that withdraw from the study should be asked about the reason(s) for withdrawal and the occurrence of adverse events, and should be examined and evaluated by the investigator according to the procedures that are defined in the Final Visit (unless reason for discontinuation is erroneous enrolment of the patient into the study at baseline and unless patient has actively withdrawn consent for any kind of future contacts).

If the patient specifically withdraws consent for future contact about the collection of further information, there will be no such contact whatsoever. However, it is possible to collect information regarding their survival status, if they are publicly available.

The investigators also reserve the right to remove a patient from the study, if according to their clinical judgment this is the necessary for the patient's welfare.

If a patient is removed or withdrawn from the study for any reason, the date, vital status and reason must be documented in the relevant section of the electronic Case Report Form (eCRF).

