- Clinical events and hospitalizations especially due to: (acute) respiratory worsening, including pneumonia, exacerbations of IPF, occurrence of pulmonary or cardiovascular complications, pulmonary rehabilitation, pulmonary embolism, pneumothorax, or cardiac failure
- Management of IPF and physician contacts

During follow up visits (prospectively until up to 2 years at least from the inclusion) 3-months (+/- 1 month), 6-months (+/- 1 month), 12-months (+/- 2 month), 18-months (+/- 2 month) and 24 months (+/- 2 months), documentation of events (or last follow up visit) will be carried out. The collection of data will be performed during standard clinical practice visits (i.e. visits should not be performed via telephone contact). In a special event where the physical presence of the patient is not possible, e.g. in case of temporary inability of the patient to visit the expert center, this visit could be performed through telephone contact and this should be recorded in patient's history. Every effort should be made, however, to ensure that the next visit will be performed as planned by the patient in person. If this is not possible the patient will be censored for the rest of the study. Patient will be followed up until death, lung transplantation, consent withdrawal or end of study, whichever comes first and will be censored if one of the events occurs. The following data will be documented:

- Clinical course of IPF (e.g. regarding symptoms, lung functionality, exercise ability, if available)
- Vital status
- Physical and vital signs examination
- Cardiopulmonary exercise testing (6-minute walk distance and CPET, if performed)
- Autoimmune Biomarker results (No additional specimen will be collected. Only already existing data will be used from exams that have been performed according to the routine clinical practice of the physicians)
- Risk of bleeding and thrombosis
- Outcomes of interest (such as acute respiratory worsening, exacerbations, hospitalization due to any cause and due to IPF). Please, refer to [Annex 3](#)
- Recording of therapeutic algorithms (change/complement/interrupt treatment) and non-pharmacological treatment (e.g. start of LTOT, new listing for lung transplantation)
- Physician's clinical rating of the probable course of IPF (stable, slow or rapid

progression)

- Assessment of treatment intensity, frequencies and resource use for pharmacoeconomic analyses for the treatments described under 11.3

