## **9.5 DATA SOURCES**

The study will mainly include the recording of new data through a web based system for data collection. Data will be collected by the study doctors as they occur according to standard clinical practice in the approximate visiting schedule indicated above.

Source (primary) patient data related to their medical and IPF history will be collected by the investigators from the patient's medical files/records and will be documented in the relevant eCRF section.

Data regarding treatment modifications, concomitant treatments, study related routine clinical assessments, adverse events (ADRs) and survival status will also be collected. If a patient withdraws early from the study, they will be contacted via telephone at the end of the Study in order to evaluate their survival status. Another follow-up assessment should be performed if possible (unless reason for discontinuation is erroneous enrolment of the patient into the study at baseline), and data should be entered on the eCRF of the next planned visit unless the patient has actively withdrawn consent for any kind of future contacts.

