#### **4. CHANGES IN THE PLANNED ANALYSIS OF THE STUDY**

As described in the study protocol only descriptive analysis will be applied for the purpose of the present study. Further to the summary tables of frequencies and measures of central tendency, Kaplan Meier curves will be produced to illustrate the survival distribution of patients in the study.

Analysis of the baseline characteristics was decided to be performed when all subjects had entered the trial.

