## **6.6 HANDLING OF MISSING DATA AND OUTLIERS**

No imputation technique to fill in any missing values will be performed. Accordingly the Last Observation Carried Forward technique will not be applied.

Missing values will be differentiated from negative answers.

Summary statistics will be performed only on subjects with available information (unknown data will not account in the total population for each specific variable).

For missing or incomplete AE dates or drug administration dates, or other significant dates, the BI internal procedures and guidelines will be employed.

Missing dates related to AE events will not be imputed since no analysis based on duration of AEs or time to event will be employed:

Missing dates related to deaths will be handled according to BI standards and therefore, no subjects with incomplete date of death will be included in the time to event analysis.

Regarding outliers, the distributional properties should be examined by PP and/or QQ plots in conjunction with the summary statistics of mean/median/SD. Should the distributional properties of a variable indicate the existence of outliers, then the values will not be neglected from the analysis, but the variance will be reduced following the logarithmic transformation. Any implausible data will be treated separately and it will be judged based on case by case basis.

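### SAP 6.6 drops patients with an incomplete date of death from the Kaplan-Meier analysis; each such death at or before month 24 raises estimated 24-month survival

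*SAP*

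**What the plan says.** SAP 4 adds one method to the descriptive summaries: "Kaplan Meier curves will be produced to illustrate the survival distribution of patients in the study". SAP 6.6 then sets the missing-data rules. In general, "No imputation technique to fill in any missing values will be performed". For deaths it refers to sponsor standards, whose text is not in the documents, and gives as their consequence that "no subjects with incomplete date of death will be included in the time to event analysis". The rule removes the whole subject, both the event and the time at risk. It makes no exception for a date known to the month, and no sensitivity analysis is planned. The sentence before it, on missing adverse event dates, says that these are not imputed "since no analysis based on duration of AEs or time to event will be employed".

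In the protocol, section 8 makes survival an aim: "this project aims to provide information regarding survival and mortality causes". Section 9.4 gives the end of follow-up: "Patient will be followed up until death, lung transplantation, consent withdrawal or end of study, whichever comes first and will be censored" if one of these events occurs. For patients who leave early, section 9.3.2 notes that "it is possible to collect information regarding their survival status, if they are publicly available", and section 9.5 says that "they will be contacted via telephone at the end of the Study in order to evaluate their survival status". Annex 3 lists the date of death as an outcome item. Annex 4, under hospitalizations, allows the discharge or death date to be recorded as unknown.

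**The concern.** A patient who is alive or lost to follow-up has no date of death and cannot be caught by this rule. It can remove only people known to have died, so membership of the analysis depends on the outcome being analysed.

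The Kaplan-Meier curve is the only time-to-event analysis in the SAP and the only one that shows how survival runs over time. With exclusions, it would contain fewer deaths than the vital-status tables, which the rule does not touch, so curve and count would disagree. A confidence interval around the curve would not cover the error, because it reflects sampling variation and not who was left out.

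**Working it through.** **Inputs.** n = 300 (Protocol 9.6). Survival is illustrative. Protocol 7.4 reports a median of 2 to 3 years from diagnosis; under exponential survival this gives S(24) = 0.5^(24/24) = 50% and 0.5^(24/36) = 63%. Section 7.4 says the median may be an underestimate, and section 9.10 says long-diagnosed patients may be more stable, so 75% is added as an assumption. The share f of deaths with an incomplete date is not in the documents; 2% to 10% is an assumed range.

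**1. The plan's own precision.** Protocol Table 2, n = 300, p = 50%: 50 ± 100 × 1.96 × √(0.5 × 0.5/300) = 50 ± 5.66, that is (44.34%, 55.66%), as printed. The same formula gives half-widths of 5.46 points at 63% and 4.90 at 75%.

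**2. Direction for a death at or before month 24.** Without censoring, removing one death changes S to S × n/(n−1). With censoring, let r₁ > … > r_k be the numbers at risk at the successive death times up to the removed death, and let h(r) = r/(r−1). Removal multiplies S(24) by h(r_k) times the product over i < k of h(r_i)/h(r_i − 1). Since r_{i+1} ≤ r_i − 1 and h is decreasing, this is at least h(r₁), and so at least n/(n−1). The month-24 estimate always rises. It fell in none of 15,034 single-death removals from random censored data sets.

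**3. Size at month 24, complete follow-up.** One dropped death: 150/299 − 150/300 = +0.17 points; 189/299 − 189/300 = +0.21; 225/299 − 225/300 = +0.25. For a share f of deaths, S′ = S/(1 − f(1−S)):

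| f | S = 50% | S = 63% | S = 75% |
|---|---|---|---|
| 2% | +0.51 | +0.47 | +0.38 |
| 5% | +1.28 | +1.19 | +0.95 |
| 10% | +2.63 | +2.42 | +1.92 |
| 95% half-width | 5.66 | 5.46 | 4.90 |

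Example: 0.50/(1 − 0.10 × 0.50) = 52.6%. In simulation with 20% independent censoring by month 24, the shifts for S = 50% and 63% were similar: about +1.3 at 5%, and +2.5 to +2.7 at 10%.

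**4. Points before the dropped deaths.** Suppose f = 10% and all dropped deaths fall in months 12 to 24. At month 12 the dropped patients were validly alive, so S′(12) = (S(12) − f(1−S))/(1 − f(1−S)). For S(24) = 50%, S(12) = 70.7% and S′(12) = (0.7071 − 0.05)/0.95 = 69.2%, a fall of 1.54 points. Simulation of 3,000 cohorts gave −1.55, −0.79 and −0.35 for the three survival values.

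**5. Deaths after month 24.** Protocol 9.3.3 allows the last visit 2 months either side of month 24, so up to month 26. Removing 5 such deaths when 150 of 300 are alive at month 24 gives 145/295 = 49.2% instead of 50.0%.

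**6. Deaths learned after withdrawal.** If they count as events, dropping one at or before month 24 acts as in step 2. If the patient is censored at withdrawal, dropping the patient removes only event-free time and lowers the estimate. With 10% to 20% withdrawing by month 24 (assumed, constant rate, independent of death) and all later deaths up to month 24 dropped, the fall is 0.1 to 0.6 points.

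**7. Check of the remedy at f = 10%, 2,000 cohorts.** Dating at the midpoint of the known month: bias within 0.02 points at months 9, 12, 15 and 24. Dating at the midpoint between scheduled visits: 0.00 at months 12 and 24, and at most about 0.7 points at months 9 and 15.

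**The case against.** The best defence is that the effect may be negligible. Annex 3 collects the date of death, Protocol 9.3.2 requires date and vital status when a patient leaves the study, and section 11.2 has fatal adverse events in nintedanib-exposed patients reported within 24 hours. At f = 2% to 5% the shift is well inside the half-width. The curve is descriptive, no 24-month estimate is named and no hypothesis is tested. All of this stands as a limit on size. It does not repair a rule that, whenever it operates, removes known deaths.

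The unseen sponsor standards might also resolve some partial dates before they count as incomplete. That is possible, so it cannot be said for certain that every death known to the month would be lost. But SAP 6.6 presents exclusion as what follows from those standards and states no exception.

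Three stronger readings are tempting and not supported:

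- A reader might infer that the rule inflates the whole curve, or that every death dropped during follow-up raises survival. Steps 4 and 5 show otherwise: points before the dropped death can fall, and a death after month 24 acts in the opposite direction.
- A reader might take the direction as settled for deaths learned after withdrawal. Section 9.4 censors at withdrawal, yet sections 9.3.2 and 9.5 deliberately collect survival status afterwards. The documents do not say which governs the curve.
- A reader might see SAP 6.6 as denying that any time-to-event analysis exists. That sentence concerns adverse event dates and does not cancel the death rule. It is a minor wording point.

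Finally, midpoint dating departs from the SAP's choice not to impute. That is true, and the remedy should say so openly.

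**Conclusion.** The concern holds in limited form. As written, SAP 6.6 selects on the outcome, and each dropped death at or before month 24 biases the month-24 Kaplan-Meier estimate upward. That direction is algebraic and needs no assumption about survival or censoring. The size depends wholly on f, which is unknown: roughly +0.4 to +0.5 points at 2%, +0.9 to +1.3 at 5% and +1.9 to +2.6 at 10%, for n = 300, complete follow-up and true survival of 50% to 75%. Earlier points can be too low, by about 1.5 points at month 12 in the most adverse case examined, and dropping deaths after month 24 lowers the month-24 estimate. If no date turns out incomplete, nothing changes. The documents do not show that the published curve will be materially wrong. They show a rule that can only misstate it and that is cheap to replace.

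**What to change.** In SAP 6.6, replace the exclusion with a rule that keeps every subject in the Kaplan-Meier analysis:

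- Count a known death with an incomplete date as an event. Date it within the interval from last known alive to first known dead, for example at the midpoint of the known month or of that interval.
- Repeat the analysis with the earliest and the latest possible dates.
- Name this as an exception to the no-imputation sentence.
- Report the number of incomplete death dates overall and by diagnosis stratum (newly or previously diagnosed).
- State that death is the event, and reconcile this with Protocol 9.4, which lists death among the reasons for censoring.
- State whether a death learned after withdrawal counts as an event or the patient is censored at withdrawal, and reconcile Protocol 9.3.2, 9.4 and 9.5 accordingly. Either way the subject stays in.
- As a tidy-up, limit the sentence on time to event explicitly to adverse events.

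The cost is one paragraph in the SAP, a clarifying sentence on the protocol sections and a little more analysis work, with no new data collection. The downside is an assumed date for a few deaths. Where only the visit interval is known, this can put the curve off by up to about 0.7 points between visits at f = 10%; the earliest and latest dates make that uncertainty visible.

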## **7.4 NATURAL COURSE**

Data on the natural course of IPF are from retrospective and a few prospective studies, including the placebo arms of clinical trials (limited to short observation periods and by in/exclusion criteria). The previously reported median survival time of 2-3 years from the time of diagnosis could be an underestimate, at least when accounting for patients with preserved lung function. Notably, the natural course is unpredictable for a given patient at the time of diagnosis, while the majority of patients experience steady worsening (slow progression), others remain stable, or have rapid progression of disease [\[10-11\]](#). Acute respiratory worsening either due to secondary complications (e.g. pneumonia, pulmonary embolism, pneumothorax or cardiac failure) or due to unknown reasons (in this case the term acute exacerbation is used) are suggested to occur in about 5-10% annually [\[1\]](#). A recent retrospective review of 461 patients with IPF has found that the 1- and 3-year incidences of acute exacerbations were 14.2% and 20.7%, respectively [\[12\]](#).

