## **7.6 ECONOMIC ASPECTS**

IPF is of high interest for the health-care system as well as for payers when considering costs. However, data on economic issues are limited, while needed for assessing cost-effectiveness of interventions [\[16-17\]](#).

The current IPF Registry will be suitable for various cost analyses. All pharmaco- and health economic parameters will be derived from either one or both of the following ways and in most cases subsequently priced:

- Assessment of the direct health resources use
- Indirect health assessment with adjustment of recorded clinical outcomes.

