9.4.5.1 Dyspnea, cough fatigue, dizziness, chest pain, anxiety [20]	x	x
Functional assessment		
Lung function test (VCin, FVC, FEV1, TLC; DLCO; pO2, pCO2) [21]		
6-minute walk distance	x	x
Cardiopulmonary exercise testing (CPET;)		
Serologic evaluation– Autoimmune Biomarkers (laboratory values)		
Rheumatoid factor, anti-cyclic citrullinated peptide, and anti-nuclear antibody titer and pattern*	x	
Others e.g. SCL-70, SS-A, SS-B		x

Proprietary confidential information © 2018 Boehringer Ingelheim International GmbH or one or more of its affiliated companies

BNP/NT-pro BNP		
Hb, AST, ALT, total bilirubin		
Pharmacological treatment( start date, stop date and daily dose)		
Past/discontinued: drugs (e.g. steroids yes/no/unknown). Detailed list of drugs in Annex 4	x	x
Current: drugs by class and/or name	x	x
Participation in IPF trial	x	x
Non-pharmacological treatment	x	x
Long-Term-Oxygen-Therapy (liquid and/or concentrate)	x	x
Lung transplantation score and assessment if the patient is currently listed for participation in lung transplantation	x	x
Physician assessment		
Physician's clinical rating of the probable course of IPF (stable, slow or rapid progression), based on available FVC results, DLCO results, physical examination, hospitalizations/events between the visits	*** x	x
Management of IPF and physician contacts		
Number of physician visits (own office, other physicians)	*** x	x
Number and type of IPF related procedures	*** x	x
Outcomes of Interest (please refer to Annex 3)		
	*** x (except for mortality, hospitalization, please see below)	x
Clinical events and hospitalizations		
specifically due to: (acute) worsening of respiratory function including pneumonia; IPF-exacerbations; manifest pulmonary or cardiovascular complications; pulmonary rehabilitation; pulmonary embolism; pneumothorax; cardiac failure (please refer to Annex 3 for detailed description of the outcomes of interest).	*** x	x
Number of days in hospital or in rehabilitation; work days lost due to IPF	*** x	x
Physical examination and vital signs		
Risk of bleeding and thrombosis	x	x

Survival status (vital status)(please refer to Annex 3)		x
--	--	---

For abbreviations, please refer to glossary.

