## **5. ENDPOINTS(S)**

### **5.1 PRIMARY ENDPOINT(S)**

The main objective of this IPF registry is to gain further knowledge on the characteristics, management, progression and outcomes of patients with IPF as treated under real-world, clinical practice conditions in Greece.

More specifically, this registry is going to:

- Provide a comprehensive clinical picture for IPF
- Track access to health care and cost of caring for IPF patients over time
- Examine the implementation of treatment guidelines, used on patients diagnosed with IPF, according to the existing diagnosis guidelines
- Characterize patients on different treatments.

Endpoints are targeting the description of the following:

- Demographic data including age, gender and race, employment status and insurance status.
- Change from baseline in vital signs as measured at 3,6,12,18 and 24 months following to the baseline visit.
- Vital Status.
- Cardiopulmonary exercise testing (6-minute walk distance and CPET, if performed)
- Change from baseline in 6-minute walk distance VO2max (CPET) as measured at 3,6,12,18 and 24 months following to the baseline visit.
- IPF risk factors as measured at baseline visit: (cigarette smoking including pack years, alcohol and substance abuse, environmental and occupational exposure, exposure to drugs associated with IPF, exposure to viral infection possibly related to IPF, gastro - oesophageal reflux, genetic factors - family history).
- Description of the comorbidities throughout the trial.
- Risk of bleeding and thrombosis as stated in the CRF.
- Description of the newly diagnosed patients of acute respiratory worsening, exacerbations, and hospitalization due to any cause and due to IPF.
- Description of the intensity of treatment, frequencies and resource utilization for pharmaco-economic analyses.
- Description of methods and procedures used in the diagnosis of IPF and time since diagnosis.
- Description of IPF symptoms (dyspnea, cough, weight loss, fatigue, dizziness, chest pain, anxiety, clubbing, bibasilar crackles)

- Description of autoimmune biomarker.
- Description of lung function and/or exercise capacity.
- Description of IPF treatment modalities.
- Description of Physician's clinical rating of the probable course of IPF (stable, slow or rapid progression).

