### **7.8.2      Laboratory data**

Summary of laboratory data (haemoglobin, AST, ALT, Total Bilirubin, BNP and NT pro-BNP) will be based on all lab data performed during the trial.

Descriptive statistics for the absolute value of all continuous evaluations and the change from baseline to study visits will be presented for each visit.

Change from baseline = post baseline value – baseline value.

The components of the *Differential Cell Count* (Lymphocytes, Macrophages, Granulocytes, Eosinophils) will be expressed as percentages (%) of the absolute cell count (e.g. lymphocytes [x/ml] / absolute cell count [y/ml])

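### SAP 6.6 orders a log transformation for any variable with apparent outliers, with no offset, exemption or reporting scale, and it cannot be carried out on zero counts or change scores

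*SAP*

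**What the plan says.** SAP 6.6 has distributions examined by PP or QQ plots together with mean, median and SD. If these point to outliers, "the values will not be neglected from the analysis, but the variance will be reduced following the logarithmic transformation". The section gives no numerical threshold, list of variables, constant to add before logging, back-transformation or scale for the tables. It also states that "Missing values will be differentiated from negative answers".

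The rule falls on the following summaries:

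- **Resource use.** The SAP 5.1 primary endpoints include "Description of the intensity of treatment, frequencies and resource utilization for pharmaco-economic analyses". Protocol 9.4.5, Table 1, collects "Number of days in hospital or in rehabilitation; work days lost due to IPF", and also numbers of physician visits and of IPF-related procedures.
- **Change from baseline.** SAP 7.8.2 sets "Change from baseline = post baseline value" minus the baseline value, and SAP 7.8.3 does the same for vital signs. SAP 5.1 also lists change in 6-minute walk distance and VO2max.
- **Continuous variables in general.** SAP 7 asks for mean, SD, median, minimum and maximum, depending on the distribution, with minimum and maximum at the precision of the recorded data. Protocol 9.8.1 also plans interquartile values and mentions no transformation.

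SAP 6.5 says that no statistical modelling will be used. SAP 4 declares Kaplan-Meier curves and the timing of the baseline analysis as changes. It mentions neither the log rule nor the quartiles.

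**The concern.** A log transformation is usually chosen to meet a model assumption or to summarise a strictly positive, skewed variable on a ratio scale. No model is planned here, and the spread of each variable is itself something the study reports. A rule that reduces variance whenever a plot looks irregular therefore alters the description without serving any stated analysis.

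The variables most likely to set off the trigger are right-skewed counts with many zeros, and these are the ones that cannot be logged. Change scores are not exempt either, and many of them will be zero or negative. The analyst would have to settle a constant, a scale or an exemption after seeing the data. The registry's tables are its result, so the reader of the report could not tell in advance what units those tables would be in.

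**Working it through.** The documents attach no figure to this rule, so there is nothing of the plan's own to reproduce. The checks below ask whether the rule can be carried out, and what follows if it is forced.

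**1. Domain.** ln(x) exists only for x > 0. Visits, procedures and days are counts and can be 0. A change, defined as post-baseline minus baseline, can be 0 or negative. Absolute values such as BNP or NT-proBNP are strictly positive and can be logged.

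**2. Counts with an added constant.** Let a share z of patients have 0 days and the rest 10 days, and let c be the constant. The back-transformed mean is

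exp[ z·ln(c) + (1 − z)·ln(10 + c) ] − c,

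and the arithmetic mean is 10·(1 − z). The zero shares, the 10-day stay and the constants are assumptions, because the documents give none of them. For z = 0.70:

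- c = 1: exp(0.7·ln 1 + 0.3·ln 11) − 1 = 1.05
- c = 0.5: exp(0.7·ln 0.5 + 0.3·ln 10.5) − 0.5 = 0.75
- c = 0.1: exp(0.7·ln 0.1 + 0.3·ln 10.1) − 0.1 = 0.30

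| Zero share z | Arithmetic mean (days) | c = 1 | c = 0.5 | c = 0.1 |
|---|---|---|---|---|
| 0.50 | 5.0 | 2.32 | 1.79 | 0.91 |
| 0.70 | 3.0 | 1.05 | 0.75 | 0.30 |
| 0.85 | 1.5 | 0.43 | 0.29 | 0.10 |

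In each row the answer varies more than twofold with a constant that the SAP does not name, and none of the values is near the arithmetic mean.

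**3. Change scores logged directly.** Assume normally distributed changes with standardised mean change d. The share with no log is Φ(−d). For about 300 patients (Protocol 9.6):

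- d = −0.5: 69%, or 207 patients
- d = 0: 50%, or 150 patients
- d = +0.5: 31%, or 93 patients

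Without the normal assumption, at least half have no log whenever the median change is zero or negative.

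**4. Visit values logged first.** The difference of logs is the log of a ratio. An equal 40 m loss in walk distance (illustrative values) gives ln(460/500) = −0.083 from 500 m and ln(160/200) = −0.223 from 200 m. Neither is the arithmetic difference that SAP 7.8.2 and 7.8.3 define.

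**5. Summary statistics side by side.** Protocol 9.8.1 has median, interquartile values, mean, SD, minimum and maximum. SAP 7 has mean, SD, median, minimum and maximum. The quartiles, which are the protocol's own way of describing skewed data, have gone, and SAP 4 does not say so.

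**The case against.** The strongest reply is that SAP 6.6 does not withdraw the SAP 7 tables. Reporting minimum and maximum at recorded precision suggests original units. If logging is only an addition, every original-unit summary can still be produced. That reading is open, and it is why the effect cannot be called certain. However, nothing in SAP 7 refers to 6.6, and 6.6 words the transformation as the handling of outliers, not as an extra table.

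On change scores, the explicit definitions in SAP 7.8.2 and 7.8.3 would naturally prevail over a general sentence, and 6.6 does not expressly order that a difference be logged. This stands as a reason for caution, but 6.6 exempts no variable. The display plan of 24 April 2020 may name a scale. SAP 7 cites it for the baseline report, so as cited it would not cover changes at follow-up.

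It is also fair that hospital admission is recorded in Protocol Annex 4 as yes, no or unknown with dates, and that the SAP 6.6 sentence on negative answers fits such items at least as well as counts. Whether patients without an admission enter a days table as zeros is not stated. Numbers of visits and procedures can be zero whatever the answer.

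Three stronger inferences are tempting and are not supported:

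- **That patients with zeros must be dropped, inflating the means.** The SAP does not say this, and other readings remain open.
- **That the protocol's cited one-year acute-exacerbation incidence of 14.2% fixes the share of zeros.** It concerns exacerbations only. Table 1 records hospital and rehabilitation days more broadly, so the zero share there is unknown.
- **That later costing would be spoiled.** Protocol 7.6 says that the economic parameters will be "in most cases subsequently priced", but the SAP specifies no costing calculation and the recorded values stay available to the sponsor.

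**Conclusion.** The point holds in limited form. SAP 6.6 sets a data-triggered log rule that no planned analysis needs and that cannot be carried out on zero-containing counts or on changes defined as differences. It names neither an offset nor a scale. If it is applied to such counts, the reported figure rests on an arbitrary constant. If it is applied to visit values before differencing, the change becomes a ratio.

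The sizes shown rest on assumed zero shares, stay lengths and distributions. They show how sensitive the result is and do not predict this registry's results. Whether any table is affected depends on the trigger being judged met, on how 6.6 is read against SAP 7, and on a display plan that was not available. No hypothesis test or decision rule is involved. The concern is therefore minor to moderate: worth correcting because the tables are the study's product. The undeclared loss of quartiles belongs in the same correction.

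**What to change.** In SAP 6.6, delete the outlier-triggered log transformation as the primary handling. In SAP 6.6 and 7, state that:

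- all plausible absolute values, counts and change scores are summarised on the original scale with n, mean, SD, median, Q1, Q3, minimum and maximum;
- zeros stay in resource-use counts, with the number and percentage of patients at zero shown;
- geometric means may be added only as a supplement, for strictly positive variables named in advance, such as BNP and NT-proBNP.

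Restoring Q1 and Q3 brings SAP 7 back to Protocol 9.8.1. If they are left out on purpose, SAP 4 should say so. If the display plan already fixes the scale and the quartiles, a sentence in SAP 6.6 and 7 stating this would be enough for the tables that it covers.

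The cost is SAP wording and a small update to table shells. No new data are needed.
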